## 10.2 Required Blood Parameters and Other Investigations Prior to Each Treatment

Before each dose of romidepsin, excluding cycle X, day 1 patients should be reassessed and the following criteria must be fulfilled:

- ANC is  $\geq 1.0$  K/ $\mu$ L.
- Platelet count is  $\geq 50$  K/ $\mu$ L.
- Serum potassium and magnesium are within normal range
  - In cycle 2 and beyond in Phase Ib and any cycle in Phase IIa, magnesium and potassium levels may be checked up to 3 days prior to administration of romidepsin. If levels are within range romidepsin may be administered without repeat testing unless clinically indicated (such as vomiting, diarrhea, or initiation of medications that may affect electrolytes).
  - Supplements must be given to patients whose potassium and/or magnesium are below normal range.
    - Magnesium supplementation: If levels are below normal range, but  $\geq 1.2$  mg/dL, patients can receive at least 2gm magnesium IV and proceed to treatment without re-checking labs. Patients can be treated if magnesium levels are above normal range.
    - Potassium supplementation: If levels are below normal range, but  $\geq 3.2$  mEq/L, patients can receive at least 20mEq potassium IV and proceed to treatment without re-checking labs.
- Any clinically significant non-hematological toxicity to  $\leq$  Grade 2 .
- ECG schedule as specified in Table 7.
- If any of these criteria are not fulfilled, then administration of study drugs should be delayed as detailed in Section 9.0.

## 10.3 Cardiac Monitoring

**Minor ECG changes are expected following romidepsin administration (refer to current Investigator's Brochure). Cardiac assessments must be performed for all study patients.** The treating investigator must perform the primary assessment and is responsible for the cardiac safety of the patients.

## 10.4 Cardiac Alert Findings (post anti-emetic)

In the event of an alert finding, the individual decision about a delay of administration, dose reduction, or withdrawal from the study will be made by the Investigator (in association with local cardiologist, if preferred). All alerts must be confirmed via manual read of the patient's ECG; the machine reading alone is not adequate. The following findings are considered to be cause for alert and if they occur, should be reported as AEs or SAEs, as appropriate:

- QTc (Bezett's—by machine read) is  $\geq 500$  msec

- QTc (Friderica's) will be used for manual reads by either the physician or cardiologist.
- If the patient has a known bundle branch block (BBB) and a baseline QTc of >470 msec a change in QTc of > 30 msec from the post antiemetic ECG will be used as criteria for an adverse event (as opposed to absolute QTc) and would be graded as a grade 3 adverse event. If no change >30 msec has been documented after completion of cycle 4 no further ECG will be required.
- If the patient has a pacemaker and a baseline QTc of >470 msec a change in QTc of >30 msec from the post antiemetic ECG in either the native rhythm or a paced rhythm will be used as criteria for an adverse event and would be graded as a grade 3 adverse event. A change can only be assessed if the rhythm is conserved (i.e. native to native rhythm). If a conversion of rhythm is seen (i.e. native to paced), and if the patient is asymptomatic no adverse event will be noted. If symptomatic it would be graded as a grade 3 adverse event. If no change >30 msec has been documented after completion of cycle 4 no further ECG will be required.
- Ventricular arrhythmia: VT ( $\geq 3$  beats in a row) or VF.
- Sinus tachycardia (pulse  $>140$ /min after recumbency).
- Heart rate is  $\geq 120$  bpm with  $\geq 20$  bpm increase from previous evaluation.
- New occurrence of atrial dysrhythmias (SVT, atrial fibrillation, or atrial flutter).
- Abnormal ST and/or T-wave changes including ST depression of  $\geq 2$  mm (as measured from isoelectric line to the ST segment at a point 60 msec at the end of the QRS complex); T-wave inversion of  $\geq 4$  mm (measured from isoelectric line to peak of T-wave) as long as the main QRS vector is positive.
- Ventricular tachycardia, including Torsade de Pointes.

See Table 6 in Section 9 for recommended dose reductions, etc., in the above situations.

## **10.5 Electrocardiograms**

An ECG must be performed within 1 hour (after administration of antiemetic premedication) prior to romidepsin and after completion of each romidepsin infusion for cycles 1 and 2. If no QTc value greater than 480 msec is demonstrated by machine-read or manual read then further ECGs may be omitted for the duration of study.

If ECG monitoring continues past cycle 2, ECGs may be omitted for the duration of the study if no QTc value greater than 480 msec is demonstrated by machine-read or manual read for two consecutive cycles and no greater than or equal to Grade 3 QT prolongation.

If a QTc of  $\geq 500$  msec is encountered, ECGs should be repeated twice more. If the mean is  $\geq 500$  msec follow dose modification guidelines in table 6.

Note to Investigators: At the Investigator's discretion, more intensive ECG monitoring can be performed for all romidepsin administrations.

## **10.6 Pregnancy Testing**

Pregnancy tests for females of childbearing potential. A female of childbearing potential (FCBP) is a sexually mature female who: 1) has not undergone a hysterectomy or bilateral oophorectomy; or 2) has not been naturally postmenopausal for at least 24 consecutive months (i.e., has had menses at any time in the preceding 24 consecutive months).

Pregnancy tests will be required by the [Revlimid REMS® program](#) and will occur within 10 – 14 days and again within 24 hours prior to prescribing lenalidomide for Cycle 1 (prescriptions must be filled within 7 days). FCBP with regular or no menstruation must have a pregnancy test weekly for the first 28 days and then every 28 days while on therapy (including breaks in therapy); at discontinuation of lenalidomide and at Day 28 post the last dose of lenalidomide. Females with irregular menstruation must have a pregnancy test weekly for the first 28 days and then every 14 days while on therapy (including breaks in therapy), at discontinuation of lenalidomide and at Day 14 and Day 28 post the last dose of lenalidomide (see Appendix C: Risks of Fetal Exposure, Pregnancy Testing Guidelines and Acceptable Birth Control Methods).

## **10.7 Follow-Up**

Patients, who discontinue treatment for any reason, will be followed for 1 month or until resolution of all treatment related AEs or initiation of alternate cancer therapy, whichever is longer. At treatment discontinuation, patients will undergo a safety assessment approximately 1 month after the last dose of protocol therapy. In addition, off study evaluations per the end of study assessments will be done.

**Table 7: Study Evaluation Schedule**

Procedure	Screening	Cycle 1				Cycle 2 and beyond**				End of study
		Day 1	Day 8	Day 15	Day 22	Day 1	Day 8	Day 15	End of cycle	
Record prior medications, treatments	X									
Record prior anti-cancer therapies	X									
Physical examination 	X	X	X	X	X 	X				X
ECOG performance status 	X	X				X				X
12 Lead ECG 	X	X	X	X		X	X 	X		
Hematology	X	X	X	X		X	X 	X		X
LDH 	X					X				
Electrolytes 	X	X	X	X	X 	X	X 	X		X
Liver function analysis 	X	X				X				X
Pregnancy testing 	X	X	X	X	X 	X				X
REMS ® program (patient enrollment)	X									
Start lenalidomide 		X				X		X		
Romidepsin 		X	X	X		X	X 	X		
Disease/Response assessment 	X								X 	
Record adverse events 		X				X		X		X
Record concomitant medications		X				X		X		X

**Table 7 Legend**

\* Romidepsin dosing may be delayed up to 3 days of the scheduled visit. Romidepsin doses must be given at least 7 days apart and all doses completed by day 21 of each cycle. In cycle 1, labs may be performed up to 1 day prior to treatment. After completion of cycle 1, labs may be performed up to 3 days prior to treatment.

\*\* For cycle 2 and beyond, study procedures should be performed per the study evaluation schedule ( $\pm 3$  days) while maintaining the minimum dosing spacing for romidepsin as above.

If Physical examination, vital signs, weight and ECOG performance status were done within 7 days of Day 1, they do not need to be repeated at study cycle X, Day 1 (excluding cycle 1 in the phase Ib portion). An unscheduled visit can occur at any time during the study.

The schedule for ECG monitoring is found in section 10.5 and romidepsin dose modifications in Table 6. After cycle 2 the schedule can be amended as clinically indicated in section 10.5.

Sodium, potassium, chloride, bicarbonate, BUN, creatinine, calcium, and glucose are part of the electrolyte assessment at every time point. **Magnesium** will be added to the electrolyte panel at **screening, days 1, 8 and 15 of the treatment cycle, and at the end of study visit**. **Liver function analysis** (at least total protein, albumin, AST,

ALT, alkaline phosphatase, total bilirubin) is necessary on day 1 of each cycle (within windows for labs provided depending on the cycle of treatment). The LDH may be omitted in patients with multiple myeloma.

Pregnancy tests for females of childbearing potential are required through the Revlimid REMS® program. A female of childbearing potential (FCBP) is a sexually mature female who: 1) has not undergone a hysterectomy or bilateral oophorectomy; or 2) has not been naturally postmenopausal for at least 24 consecutive months (i.e., has had menses at any time in the preceding 24 consecutive months). Pregnancy tests must occur within 10 – 14 days and again within 24 hours prior to prescribing lenalidomide for Cycle 1 (prescriptions must be filled within 7 days). FCBP with regular or no menstruation must have a pregnancy test weekly for the first 28 days and then every 28 days while on therapy (including breaks in therapy); at discontinuation of lenalidomide and at Day 28 post the last dose of lenalidomide. Females with irregular menstruation must have a pregnancy test weekly for the first 28 days and then every 14 days while on therapy (including breaks in therapy), at discontinuation of lenalidomide and at Day 14 and Day 28 post the last dose of lenalidomide (see Appendix C: Risks of Fetal Exposure, Pregnancy Testing Guidelines and Acceptable Birth Control Methods).

Lenalidomide must be prescribed through and in compliance with the REMS® program of Celgene Corporation. Prescriptions must be filled within 7 days. Consideration should be given to prescribing lenalidomide 5 to 7 days in advance of Day 1 of each cycle to allow time for required patient and prescriber surveys, and drug shipment to patient. Any unused Revlimid® (lenalidomide) should be returned to Biologics for disposal in accordance with the REMS® program.

Baseline disease assessments must be performed after discontinuation of most recent anti-cancer therapy including systemic steroids. Outside scans are acceptable if performed within 28 days.

 Lymphoma: CT including at least the chest, abdomen and pelvis or PET/CT is required for response (systemic B and T-cell lymphoma patients only) assessment. A bone marrow will only be repeated to confirm a complete response if previously known to be involved. Cutaneous T-cell lymphoma patients will have imaging at baseline and (CTCL) will have an mSWAT (Appendix I) performed monthly for the first three cycles and then at each response assessment timepoints (end of cycle 4, 6 and thereafter at the end of every third cycle). In CTCL patients, imaging will be repeated if appropriate (patients with known nodal or visceral disease) every other cycle. Sezary panel in patients with Sezary syndrome. Cutaneous lymphoma patients without nodal or visceral disease will have imaging repeated only to confirm a complete response. After cycle 12, patients on continuous therapy may be imaged as clinically indicated, at the discretion of the treating physician. At discontinuation of therapy, end of study response assessments – including imaging – should be performed.

Serum/urine protein electrophoresis, serum/urine immunofixation, quantitative immunoglobulins, and serum free light chains are required if appropriate for (multiple myeloma patients only) response assessment. A bone marrow will only be repeated if to confirm a complete response. Patients with non-secretory myeloma will have the bone marrow assessment repeated if they have been otherwise clinically stable (i.e. without new lytic lesions, soft-tissue plasmacytomas or hypercalcemia). A skeletal survey is allowed to rule out bone lesions for evaluation of disease progression and to confirm a complete response in nonsecretory multiple myeloma. PET/CT should be performed at screening and to confirm responses in patients with soft tissue plasmacytomas.

 An additional safety assessment will be done 28 days (+/- 2 days) following the last dose of protocol therapy.

 If romidepsin is omitted on day 8 per dose reduction algorithm (Table 4) then hematologic and electrolyte assessments are not required.

Response assessment will be performed at the end of cycles 2, 4, and 6. Thereafter, response assessment will occur at the end of every third cycle (9,12,15, etc.) until disease progression or removal from study. Myeloma patients will have their disease assessed after each cycle.

 +/- 3 days

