## 2.0 OBJECTIVES AND SCIENTIFIC AIMS

### **The primary objectives of this study are:**

- To define the maximum tolerated dose and characterize the safety and toxicity of the combination of lenalidomide and romidepsin.

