## 4.0 OVERVIEW OF STUDY DESIGN/INTERVENTION

### 4.1 Design

**Phase Ib:** The phase Ib portion of the study is designed to determine the MTD of romidepsin and lenalidomide. All patients must have a relapsed or refractory B-cell lymphoma, T-cell lymphoma, or multiple myeloma. Patients will be treated on a 28-day cycle with romidepsin infused on day 1, 8, and 15, and lenalidomide taken orally on days 1-21. The design is a standard 3+3 dose escalation (Table 1) of romidepsin and lenalidomide. The first cohort will enter at dose level 1.

Dose Level	Romidepsin	Lenalidomide
-1	8 mg/m 	10 mg
1	8 mg/m 	15 mg
2	8 mg/m 	25 mg
3	10 mg/m 	25 mg
4	14 mg/m 	25 mg

Table 1: Description of dose level

DLT is defined in cycle 1 (in phase Ib).

Definitions:

- Grade  $\geq$  3 non-hematologic (attributed to study drugs)
- Grade 4 hematologic toxicities (attributed to study drugs) defined as:
  - Grade 4 thrombocytopenia (platelets  $< 25$  K/ $\mu$ L)
  - Grade 4 neutropenia (absolute neutrophil count (ANC)  $< 0.5$ )
- Grade 3 thrombocytopenia or neutropenia that results in a  $> 3$  day delay in any romidepsin dose in cycle 1.
- One week or greater delay in initiating cycle 2 day 1 due to continued drug-related toxicity.

Any patient with an adverse event that meets the DLT definition is considered evaluable for MTD determination. Patients who do not have a DLT, but received  $<3$  doses of romidepsin or  $<80\%$  (17/21) of the doses of lenalidomide during cycle 1 will not be evaluable for MTD and will be replaced.

Three patients will be initially treated in each cohort until the MTD is determined. If dose level 4 (full dose of each drug) is achieved without DLT after 1 cycle that dose level will be deemed the optimal dose and the study will proceed to a phase IIa expansion cohort. Patients treated at MTD in the phase Ib portion will be counted towards the phase IIa accrual by disease subtype and also for all efficacy and toxicity endpoints unless they did not have measurable disease at point of study entry as allowed in the phase Ib portion.

**Phase IIa:** The phase IIa portion will further assess the toxicity and safety and allow a preliminary assessment of the efficacy of the combination to provide background for a potential future subtype specific phase II study (see Section14.0).

DLT is defined in cycles 1-4 (in phase IIa)

Definitions:

- Grade  $\geq$  3 non-hematologic (attributed to study drugs)

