### **11.4 Other Risks**

Patients should be instructed that if any physician other than the study doctor prescribes medication for another condition, or patients start to take any over-the-

counter medications or vitamins, they must inform the study staff. This is important because the interaction of some medications may cause serious side effects.

- Patients taking lenalidomide and dexamethasone for multiple myeloma should be careful taking drugs that may increase chance of having blood clots.
- Cases of transient liver laboratory abnormalities were reported in patients treated with lenalidomide.
- Lenalidomide has been shown to increase the level of digoxin in the blood in some patients.

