## 14.0 BIOSTATISTICS

The standard dose-escalation scheme for this study is as follows. Patients will be accrued to the study in cohorts of 3. For any given dose an initial cohort of 3 patients will be treated at that dose. The dose level will be escalated if none of the 3 patients exhibits any DLT in the first cycle as defined in section 4.1. If a DLT is observed in one patient, an additional cohort of 3 patients will be treated at that dose. The dose will be escalated if none of the additional 3 patients exhibits any DLT. Dose-escalation stops and the previous dose will be considered the MTD if 2 or more patients have a DLT. If the previous dose level has been administered to only 3 patients, an additional 3 patients will be enrolled to confirm the result. For this design the probability of escalation is as follows:

True toxicity rate	5%	10%	15%	20%	25%	30%	40%	50%
Probability of escalation	0.97	0.91	0.81	0.71	0.60	0.49	0.31	0.17

Dose escalation will start with dose level 1. A dose level -1 is also added to the design to ensure a minimum level of toxicity (we expect this dose level will be quite tolerable for patients). The maximum number of patients needed for this dose escalation design is 30. Patients with measurable disease treated at MTD in the phase Ib will be analyzed in phase Ila to further characterize the toxicity of romidepsin and lenalidomide in combination at the MTD determined by phase Ib. In phase Ila, we plan to enroll about 39 patients so that the total number of patients to be treated at MTD will be approximately 44 (we plan to enroll 15 patients with B-cell lymphomas, 8 patients with multiple myeloma, 15 patients with T-cell lymphomas and additional 6 patients with acute T-cell leukemia/lymphoma). To subsequently monitor the safety primary endpoint in the phase Ila portion, we will employ a dose-reduction plan for the predefined DLT in the phase Ib portion during cycles 1-4. This dose-reduction plan specifies that the dose will be reduced from the phase Ib MTD to the MTD-1 (10mg/m^2 romidepsin; 25mg lenalidomide) if DLT occur in cycle 1-4 in: ≥8/first 15; ≥16/first 30; or if more than 24 patients when the last (45th) evaluable patient has completed the trial have any DLT. If at MTD-1 a DLT occurs in ≥8/first 15; ≥16/first 30, then MTD-2 (8mg/m^2 romidepsin; 25mg lenalidomide) will be employed for the remainder of phase Ila. The probability of dose-reducing from the MTD is the following:

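### No scheduled liver test falls between Day 1 visits, so a hepatic DLT that rises and recovers within a cycle can be missed and the observed DLT rate can only be biased downward

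*Combined protocol and SAP*

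**What the plan says.** **Endpoint.** The primary objective (Section 2.0) is "To define the maximum tolerated dose and characterize the safety and toxicity of the combination of lenalidomide and romidepsin". Section 4.1 lists as its first DLT criterion an event of grade ≥ "3 non-hematologic (attributed to study drugs"). The same criterion appears for both phases. For phase Ib, "DLT is defined in cycle 1 (in phase Ib"); for phase IIa the window is cycles 1-4.

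**Decision rule.** Section 14.0 says of phase IIa that "we will employ a dose-reduction plan for the predefined DLT in the phase Ib portion during cycles 1-4". The dose is reduced at 8 or more DLTs in the first 15 patients, 16 or more in the first 30, or more than 24 at the 45th.

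**Sampling.** The Table 7 row "Liver function analysis" is marked at screening, cycle 1 Day 1, Day 1 of later cycles and end of study. Footnote 3 agrees: "ALT, alkaline phosphatase, total bilirubin) is necessary on day 1 of each cycle". Electrolytes, a panel that includes creatinine, are also drawn on Days 8 and 15 of each cycle and on Day 22 of cycle 1.

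**Known risk.** Section 11.4 states: "Cases of transient liver laboratory abnormalities were reported in patients treated with lenalidomide". Section 11.1 lists raised liver enzyme tests among the less likely effects of romidepsin, and Section 11.2 lists abnormal liver function tests among the less likely effects of lenalidomide.

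**The concern.** The DLT definition covers a whole window, but the only scheduled means of finding a hepatic laboratory DLT is a sample at the ends of each cycle. The cycle 1 Day 1 sample is a pre-treatment value. For a patient who continues, the first scheduled result after dosing is at cycle 2 Day 1. A grade 3 rise that has come down by then leaves no scheduled record. If nothing else prompts a test and the patient has no other DLT, the patient is scored as DLT-free and, with adequate dosing, as evaluable.

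This error runs one way: missed events lower the observed DLT rate. In phase Ib they make escalation more likely. In phase IIa they make the 15/30/45 rule less likely to trigger. The myeloma rule in Section 9.3 (two DLTs in six or fewer patients) has small denominators, so a single missed event can matter there too. Both probability tables in Section 14.0 implicitly assume that every DLT is observed.

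**Working it through.** **1. Timing of the first post-dose liver result.** From Sections 4.1 and 4.2: romidepsin on Days 1, 8 and 15, lenalidomide on Days 1-21, cycle length 28 days. Cycle 2 Day 1 is Day 29.
- Since the last romidepsin dose: 29 − 15 = 14 days.
- Since the last lenalidomide dose: 29 − 21 = 8 days, which is 7 full days off drug.
- The Table 7 legend allows labs up to 3 days earlier (Day 26), giving 11 and 5 days.

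So the sample falls roughly two weeks after the last romidepsin dose and one week after the last lenalidomide dose, if doses are on schedule.

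**2. What else could detect the event.**

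| Provision | What it can show |
|---|---|
| Section 10.1, AST/ALT limits before a new cycle | Events not recovered by the next Day 1 |
| Section 10.2, checks before Day 8 and Day 15 romidepsin | Names ANC, platelets, potassium, magnesium, ECG and clinically significant non-hematologic toxicity; no liver test |
| Table 7, examinations on Days 8, 15 and 22 of cycle 1 | Symptoms or signs; no mid-cycle examination is scheduled from cycle 2 on |
| Table 7 legend, unscheduled visits | Events that something else has prompted |

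None is a scheduled test for a laboratory rise without symptoms.

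**3. Reproducing the plan's figures.** With true DLT probability p, q = 1 − p and X_n binomial(n, p):

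- Escalation = q³ + 3pq² × q³. At p = 0.30: 0.343 + (3 × 0.30 × 0.49) × 0.343 = 0.494 (plan: 0.49). All eight entries reproduce.
- Dose reduction = P(X15 ≥ 8) + P(X15 ≤ 7, X30 ≥ 16) + P(X15 ≤ 7, X30 ≤ 15, X45 ≥ 25). At p = 0.30, 0.35, 0.40 and 0.50 this gives 0.052, 0.122, 0.241 and 0.607 (plan: 0.056, 0.118, 0.243 and 0.632). Eight of the nine entries agree within 2 points. The 50% entry is 2.5 points off and fits a final boundary of 24 or more (0.630) better than the stated more than 24. That is a separate matter and does not change this point.

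**4. Effect of missed events.** Assumption: m is the percentage of all patients whose *only* DLT is a hepatic event that no test picks up. A patient with any other DLT is already counted. The rule then acts on p − m.

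| True rate | Quantity | m = 0 | m = 1 | m = 2 | m = 5 |
|---|---|---|---|---|---|
| 30% | Dose reduction | 0.052 | 0.043 | 0.035 | 0.018 |
| 40% | Dose reduction | 0.241 | 0.213 | 0.187 | 0.122 |
| 50% | Dose reduction | 0.607 | 0.567 | 0.527 | 0.410 |
| 30% | 3+3 escalation | 0.494 | 0.515 | 0.536 | 0.600 |

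At a true 25% rate the dose-reduction probability is already only 0.018. Losing 5 points takes it to 0.004, so the 15/30/45 rule is practically unaffected at 25% or below.

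**The case against.** The strongest reply is that Day 1 is a required minimum, not a ceiling. Investigators may test at any time, patients are examined weekly in cycle 1, Section 17.2.1 requires all adverse experiences to be recorded, and Section 10.1 stops a new cycle if AST or ALT is still too high. This stands to the extent that it would be wrong to infer that such events can never be seen. The documents support only that no *scheduled liver test* detects them. A rise without symptoms that has recovered by the next Day 1 still escapes all these provisions.

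A reader might also infer that Section 10.2 demands a liver check for which no sample is scheduled. It does not. Its wording is "Any clinically significant non-hematological toxicity to" grade 2 or lower; it names no liver test and leaves clinical significance to judgment. There is no contradiction between Section 10.2 and Table 7, only a gap between the DLT definition and the sampling schedule.

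On size, the objection is largely right. Section 11.4 gives no grade, rate or duration and concerns lenalidomide only. The severe-toxicity rates quoted in Section 3.0 are for blood counts and infections, not liver events. Nothing in the documents says that hepatic events are usually silent or when they recover. One could take ten points off a 40% rate and read a fall from 0.243 to 0.056 in the plan's table, but that needs one patient in ten to have a missed hepatic event as the only DLT, and the documents give no basis for it. A rise that recurred over several cycles would also give the Day 1 tests more than one chance.

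Finally, Section 9.3 says the lymphoma MTD is already determined, and Sections 4.1 and 14.0 pool measurable-disease phase Ib patients treated at the MTD with phase IIa. Changing the sampling now would put two detection schemes into one rate. That is a real cost, and the fix addresses it.

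**Conclusion.** The point holds in a limited form. An attributed hepatic laboratory event of grade 3 or higher that rises and recovers between Day 1 visits is a DLT under Section 4.1, but no scheduled liver test detects it. Any resulting bias in the DLT rate is downward. That direction follows from the documents; the size does not. Under the stated assumption of 1 to 5 percentage points of hepatic-only missed DLTs, the dose-reduction probability at a true 40% rate drops by 0.028 to 0.119 (0.241 − 0.213 and 0.241 − 0.122). With 5 points missed at a true 30% rate, the escalation probability rises by 0.106 (0.600 − 0.494). At 25% or below the phase IIa rule is essentially unchanged.

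This does not show that the MTD was wrongly chosen or that hepatic DLTs were in fact missed. It is a limit on ascertainment of the primary safety endpoint that is inexpensive to narrow and should otherwise be disclosed.

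**What to change.** Amend Table 7 and footnote 3 so that AST, ALT and total bilirubin are run on the chemistry sample already drawn on Days 8 and 15 of cycles 1-4 and on Day 22 of cycle 1. The existing DLT definition then applies unchanged. Where footnote 10 waives the Day 8 sample because romidepsin is omitted that day, there is no sample to use, and cycles 2-4 have no Day 22 sample, so some gap remains.

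For patients treated before the change, report that during treatment liver tests were scheduled only on Day 1 of each cycle. If they are pooled with later patients, show the DLT rate by monitoring scheme.

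The cost is one amendment and the assay fees, with no new scheduled visit or venepuncture. The downsides are some additional laboratory-only DLTs, which enter the existing dose-modification rules of Section 9.7, and two ascertainment schemes within the pooled MTD cohort.
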